## **C. APPROACH**

**Overview.** Given the underwhelming use of MBC in community mental health settings coupled with the demand for performance outcome assessment (Affordable Care Act), this randomized implementation trial aims to compare the effectiveness of a standardized versus tailored approach to implementation of MBC with co-primary outcomes at the clinician (MBC fidelity) and client (depression severity) levels. We will randomize 12 sites of a large community mental health center (Centerstone) to early or later stage standardized or tailored implementation enrolling 150 clinicians and 500 depressed clients in a pragmatic trial (Thorpe et al., 2009). The main clinician level outcome is MBC fidelity, defined as (a) client completion of the PHQ-9, (b) clinician review of scores in the electronic health record, and (c) discussion of scores in session. Phase 1 (months 0-8) will interface the most widely used and validated depressive symptom severity measure (Patient Health Questionnaire-9 item; PHQ-9; [name], 2001) with the electronic health record; this measure is the main client level outcome. Phase 2 (months 8-38) constitutes the active implementation (5 months) and sustainment (10 months) phase. In both conditions, clients will have the option to complete the PHQ-9 on tablets in the waiting room prior to session, which will feed scores to clinicians via the electronic health record. Sites randomized to the standardized condition will begin with a baseline mixed methods needs assessment (for the purposes of putative mediator data collection) and receive the guideline that MBC is to be used in each session with a depressed client. The standardized condition will include manualized training and triweekly group consultation with experts to promote MBC fidelity and optimize its clinical utility. An implementation team (including a site administrator, opinion leader, MBC champion, and research personnel) will convene prior to each triweekly group consultation to review progress and troubleshoot problems. Sites randomized to the tailored condition will also begin with a needs assessment to identify contextual factors that may serve as barriers to the implementation (guided by the *Framework for Dissemination*; [name] et al., 2008; see C7). Training and triweekly group consultation will be tailored to address these barriers (e.g., clinician attitudes toward MBC). The implementation team (same composition as in standardized) will define a site-specific guideline for MBC use (e.g., monthly) and convene prior to each triweekly group consultation to troubleshoot MBC fidelity barriers. At the start of the active implementation across both conditions, depressed clients of participating clinicians will be enrolled to compare the effect of standardized versus tailored MBC implementation on client outcomes. Phase 3 (months 38-48) will characterize MBC fidelity using electronic health record data capture. The evaluation approach is guided by the *Framework for Dissemination* ([name] et al., 2008) and includes a baseline needs assessment, implementation/process evaluation (5 months into implementation), and outcome/impact evaluation (15 months into implementation). This design will allow for a direct test of the assumption that voltage drop in treatment outcomes occurs in the context of adapting the intervention to fit the context (Chambers et al., 2014), while simultaneously exploring the effect of standardized and tailored approaches to MBC implementation.

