**Tailored Implementation Condition.** Tailored Implementation refers to the [responsive application of implementation strategies and content matched to determinants of practice \(i.e., barriers\) identified via a needs assessment](#). The same strategies outlined in the standardized condition will be employed in the tailored condition, but with content tailored to the site. The needs assessment will reveal contextual factors that may serve as barriers to the implementation process (focus groups will be analyzed using rapid ethnography methods; [C13b. Qualitative and Mixed Methods Data Analysis Plan](#)). An implementation team will convene to define the site-specific guidelines for PHQ-9 completion. For instance, it may be that Site X decides that monthly PHQ-9 administration is optimal with respect to feasibility and clinical utility. Conversely, Site Y may prefer to have clients complete the PHQ-9 every other session. Depressed clients of clinicians in the tailored condition will complete the PHQ-9 in the waiting room on a tablet computer prior to their appointment with the enrolled clinician based on the site-specific administration guideline. PHQ-9 data will then be fed to the electronic health record for clinician review. Training will be offered to all enrolled clinicians using tailored materials that will target the identified barriers from the needs assessment. For instance, if clinicians at a particular site perceive the PHQ-9 to be irrelevant to clients, training content will incorporate client perspectives on its utility. If clinicians indicate that lack of time is a barrier, then training will incorporate experimentation to streamline review and discussion of scores. The implementation team will focus on identifying remaining barriers for discussion in the triweekly group consultation session. Similar to the standardized condition, consultation will also focus on incorporating clinician review and discussion of PHQ-9 scores in session and providing tips on targeting lack of progress.

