**Phase 2: Randomized Trial: Implementation & Sustainment.** Implementation will take place across 12 sites in months 8-38 using the dynamic waitlist control design (Brown et al., 2006; C15. Justification and Feasibility). Specifically, matched sites (based on size and urban/rural status) will be randomized to either early or later stage implementation in 4 cohorts (2-4 sites per cohort spaced 5 months apart), with half the sites randomized to the standardized and half to the tailored condition; see Figure 2 for a concise depiction of the implementation timing. The timing of this protocol is based on the published work of Miller et al. (2012) as well as the successful naturalistic MBC implementation at Group Health (personal communication, [name], February 11, 2014). Beginning at month 8, the earliest cohort (2 sites) will engage in the baseline mixed methods needs assessment (Assessment Time 1; AT1). Using purposeful sampling (Palinkas et al., 2013), a subset of clinicians (N=5-8 at each site) representing extreme variation (nominated by clinic directors based on their support for or against MBC implementation) will participate in a 1.5-hour focus group. This sampling approach is critical to gain a wide range of clinician views. Rapid ethnography will then be used to uncover site-specific insights that will guide the content of training and consultation in the tailored condition only (with the aid of mixed method expert [name]; C13b. Data Analysis Plan). During the needs assessment, all enrolled clinicians will complete the battery of baseline measures (see Table 5, Section II), from which the opinion leader (Childers, 1998) and self-nominated MBC champion will be identified and invited to join the implementation team. Across conditions, this team will convene triweekly during the 5-month active implementation period to ensure implementation strategy fidelity (Proctor et al., 2013) and review MBC fidelity. Following the needs assessment, clinicians will participate in a 4-hour MBC training workshop (see C9. Pilot Studies for content) and will begin triweekly consultation. To characterize the differences in implementation team meetings and consultation between conditions, sessions will be audiorecorded and contextual factors logged by graduate research specialist on the MBC Barriers Log (informed by the Framework for Dissemination; [name] et al., 2008; see Appendix for form template). Simultaneously a site team member will log meetings (using the same form) and data triangulated to calibrate site team members and prep for the exit of research personnel. Implementation/Process Evaluations ([name] et al., 2008; AT2) at the clinician level will occur 5 months after the needs assessment at which point the research personnel will be removed. The site implementation teams will be encouraged to continue meeting to promote MBC sustainment and the responsibility to log and address MBC barriers will transfer completely to the site team members. Outcome/Impact Evaluation ([name] et al., 2008; AT3) at the clinician and client level will occur 10 months after the Implementation/Process Evaluation. Focus groups will be held with the implementation team at AT3 to review their experience and the site's progress since the research personnel exited the team. All aforementioned steps will be repeated across the remaining three cohorts.

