**Aim 1: Hypotheses:** Tailored implementation will outperform standardized in terms of (H1a) fidelity. MBC clinician fidelity was evaluated with two variables: (1) whether the PHQ-9 was recorded in the EHR, and (2) among encounters for which the PHQ-9 was recorded, whether it was discussed. Both outcomes were modeled using generalized linear mixed models with a logit link function for a binary distribution using the lme4 package. All models included random intercepts for clinicians and patients. Models for both outcomes were constructed in an identical sequence. Models comparisons in the model-building sequence described below were evaluated using the Bayesian Information Criterion (BIC); the model with the better BIC was selected for presentation. Several unconditional growth models (i.e., models with only parameters for time) were fit (i.e., linear, quadratic, log-transformed number of months). After establishing the unconditional growth model, additional fixed effects were added in the following sequence: (1) group main effect and (2) group x time interaction. Finally, new versus existing patient status was investigated as a main effect using a dummy variable for new patient status and as a patient status x group interaction.

**Aim 2: Hypotheses:** Contextual mediators will be leveraged in the tailored condition, but serve as barriers in the standardized condition. Mediation models were fit to evaluate which contextual factors (based on clinician-completed surveys, Table 5; and, clinician selection of drop-down menu reasons for MBC deviations captured in the electronic health record) mediate the impact of the implementation condition on both clinician- and client-level outcomes. The two critical effects underlying mediation were evaluated in separate models: treatment condition predicts the mediator (path *a*) and the mediator predicts the outcome (path *b*). Specifically, mediators were assessed at the conclusion of the implementation window and the mediators were used to predict PHQ9 completion in the sustainment window. The *a* path was assessed using linear mixed models with Satterthwaite degrees of freedom

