implemented using the R lmerTest package with a random intercept for clinic. The b path was assessed using generalized linear mixed models with a logit link function for a binary distribution using the lme4 package. **Aim 3 Hypotheses:** Adapted MBC protocols (i.e., tailored condition) will outperform routine weekly administration of PHQ-9s (i.e., standardized condition) with respect to clinically significant change in depression severity from intake to week 12. Depression severity was analyzed using linear mixed models with Satterthwaite degrees of freedom implemented using the R lmerTest package. Multiple imputation was used to estimate missing values across 20 datasets in which 22.8% of patients did not complete the 12-week interview. We first assessed whether there was a change in PHQ-9 between intake and week 12 in a mixed model containing patient status as a covariate and random intercepts for patient and clinic. Next, implementation group was added to the model. In addition, number of sessions, number of sessions that the PHQ-9 was recorded, and number of sessions that the PHQ-9 was discussed were added to the model. We also examined the interactions between new patient status and the focal variables. **Power calculations.** A power analysis for the multilevel models for Aim 1 was assessed with Monte Carlo studies in which power is the proportion of significant effects (2-tailed  $\alpha$ ,  $p < .05$ ) for parameters of interest observed over repeated analyses of simulated data (Muthén & Muthén, 2002; Thoemmes, Reiser, & MacKinnon, 2010) using MPlus (version 7). For each model, 10,000 data sets were simulated and analyzed. Data in the Monte Carlo studies were simulated with the goal of identifying the smallest detectable effect size with power  $> 80$ . Dropout was simulated to reflect an increase of 5% missing data per wave. Repeated measurements were nested within participants (ICC = .50) and participants were nested in sites (ICC = .05). Average effect sizes for Aim 1 analyses were computed using an approximation of Cohen's  $d$  for growth models (Feingold, 2009). Using this metric, we are sufficiently powered to detect effect sizes as small as  $d = .46$  for the clinician models ( $N = 150$ ) and effect sizes as small as  $d = .30$  for the client models ( $N = 500$ ). For Aim 2, we conducted power analyses for the hypothesized mediation effects with the same assumptions described above but with the use of effective samples size estimates (an ICC corrected sample size) based on a design effect adjustment (Bickel, 2007) in order to use standard effect size metrics. The  $\kappa^2$  effect size for mediation (.01, .09, and .25 represent small, medium, and large  $\kappa^2$  respectively) was computed (Preacher & Kelly, 2011). We are sufficiently powered to detect effect sizes as small as  $\kappa^2 = .16$  for the clinician models and effect sizes as small as  $\kappa^2 = .10$  for the client models. For Aim 3 analyses, we are sufficiently powered to detect effect sizes as small as  $r = .27$  for clinicians and as small as  $r = .21$  for clients. The planned sample sizes are consistently sufficient for detecting medium effect sizes for clinician outcomes and small effect sizes for client outcomes, with the power to treat site as a random effect based 6 sites per condition (Atkins & Baldwin, 2013).

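### Aim 2 path a averages each contextual factor over all six tailored sites although tailoring targets site-specific barriers, so null results across factors would not show that contextual factors do not mediate.

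*Combined protocol and SAP*

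**What the plan says.** C13a, Aim 2, splits mediation into two models: "The two critical effects underlying mediation were evaluated in separate models: treatment condition predicts the mediator", and then the mediator predicts the outcome. Path a is a linear mixed model "implemented using the R lmerTest package with a random intercept for clinic". On timing, "mediators were assessed at the conclusion of the implementation window", which is AT2. No term records whether a site had a factor as a barrier or worked on it, and adjustment for the baseline score is not mentioned.

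C10 describes the tailored arm: "Training will be offered to all enrolled clinicians using tailored materials that will target the identified barriers from the needs assessment". C11, Phase 2, adds: "Rapid ethnography will then be used to uncover site-specific insights that will guide the content of training and consultation in the tailored condition only". In the standardized arm, the Overview in section C says that sites also "begin with a baseline mixed methods needs assessment (for the purposes of putative mediator data collection"), so baseline data on the factors exist in both arms.

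C14 says that failure to detect mediators may be a reason to re-evaluate the Framework. Section A classes Aim 2 as secondary and exploratory.

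**The concern.** Tailoring is meant to do different things at different sites. The pilot in C9 shows why. One site found MBC artificial and too evaluative of clinicians; the other worried about productivity, feasibility and utility. The two sites differed by d = 0.71 and 0.95 on two attitude subscales.

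The planned path a asks whether a given factor moved on average over all tailored sites. Suppose tailoring removed each site's own barrier, but any one factor was a barrier at only a few sites. Most factor-level tests could then be null although the mechanism worked. Read through C14, that pattern would count against the Framework when it may only reflect averaging.

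**Working it through.** **Inputs from the documents.** 12 sites, 6 per condition; 150 clinicians, so 150/12 = 12.5 per site; site ICC .05; repeated-measures ICC .50; two-sided alpha .05; stated detectable clinician mediation effect κ² = .16 (all in C11 to C13a).

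**Assumptions.** The number s of tailored sites that target a factor, and the shift δ at those sites, are not given. I take s = 1 to 6 and δ = 0.5 and 0.8 SD, all-or-none, with equal site sizes.

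**1. The plan's own figure.** Design effect = 1 + (12.5 − 1) × .05 = 1.575; effective N = 150/1.575 = 95.2. If κ² = .16 is mapped to equal standardized paths with no direct effect, a = b = .409. The first-order product test then has 82.9% power, or 78.7 to 80.3% with 10% missing. So .16 reproduces. It implies a path a effect of d = 2(.409)/√(1 − .409²) ≈ .90. The power statement does not consider effects that differ between tailored sites.

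**2. Path a when only s sites move.** With balanced sites the random-intercept model is a t test on site means with 10 df. With 12 clinicians per site:

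- variance of a site mean = .05 + .95/12 = .129
- standard error of the arm difference = √(2 × .129/6) = .207
- expected effect = (s/6) × δ
- expected addition to the tailored arm's between-site variance = δ² × s(6 − s)/(6 × 5), half of which enters the pooled variance

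Example, s = 3 and δ = 0.8: the effect is 0.40. The added variance is .64 × 9/30 = .192, so the pooled variance is .129 + .096 = .225 and the standard error √(2 × .225/6) = .274. The ratio is 0.40/.274 = 1.46, against a critical value of 2.23. At s = 6 the ratio is 0.80/.207 = 3.86.

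Simulated power of the planned path a:

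| s of 6 | 1 | 2 | 3 | 4 | 5 | 6 |
|---|---|---|---|---|---|---|
| δ = 0.5 | 5% | 8% | 13% | 23% | 39% | 59% |
| δ = 0.8 | 5% | 9% | 21% | 42% | 71% | 93% |
| δ ≈ .90 (from κ² = .16; 12.5 per site) | 4% | 10% | 23% | 49% | 80% | 98% |

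**3. AT1 adjustment of the same models.** Variances: site .05, stable clinician .45, occasion .50. At s = 6 and 0.5 SD, power rises from about 59% to about 79%. At s = 2 and 0.8 SD it stays near 10%. Adjustment gains precision but does not cure dilution.

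**4. Site-specific mediator.** At all 12 sites, take the worst of six factors at AT1 and compare its AT1-to-AT2 change between arms. Type I error is 5%. Power depends on how often the rule picks the barrier that was actually targeted:

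| Concordance | 0.5 SD | 0.8 SD |
|---|---|---|
| 100% | 81% | 99% |
| 75% | 46% | 69% |
| 50% | 22% | 34% |

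**The case against.** A reader might infer that path a will be null for most or all factors and that H2 therefore goes unanswered. The documents do not support either inference.

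- **Sharing of barriers is unknown.** Some arm differences are built in at every tailored site: Table 3 has the guideline set by the site and the team focused on barriers. C10 speaks of barriers in the plural, so one site may target several factors. Part of the consultation content is common to both arms, so tailored sites do not work only on their own barriers. Practicality attitudes at the two pilot sites were close (3.03 and 3.14). For widely shared factors s may be 5 or 6.
- **The averaged contrast is valid.** It is a randomized estimate of the condition effect on each factor, and C13a asks which factors mediate. A site-specific mediator cannot name one.
- **C13b adds qualitative work** within each site, and C14 relies on it to examine mediators that were not anticipated.
- **A site-specific test can be diluted too.** Barriers are identified from focus groups by rapid ethnography, not by ranking survey scores, so concordance may be modest.

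All four points stand. They rule out replacing the planned models as the lead test. They do not remove the gap: the quantitative plan never links a factor to the sites that worked on it, and the qualitative analysis is not a test of path a.

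**Conclusion.** The point holds as a limit on what the planned test can show. It is not a claim that the test is invalid or certain to fail. At 0.8 SD, path a misses more often than not when four or fewer of six tailored sites target the factor, and has 71 to 93% power at five or six. At 0.5 SD it misses more often than not at five or fewer; the 59% at six sites reflects the small number of clusters, not dilution. These figures rest on assumed s and δ, all-or-none shifts and equal site sizes; C12a gives sites of 12 to 52 clinicians, and imbalance would lower power.

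What follows is about interpretation: nulls across the factors would not establish absence of contextual mediation, and do not by themselves support the re-evaluation that C14 contemplates.

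**What to change.** 1. Keep the factor-by-factor path a models and adjust each for the AT1 score already collected.
2. Add one supplementary analysis. At every site in both conditions, select the worst one or two factors by a single rule that uses AT1 data only. Analyse the clinician's AT2 score on those factors, adjusted for AT1, with the clinic random intercept. Using the same rule in both arms preserves the randomized comparison and makes regression to the mean alike.
3. From the MBC Barriers Log, report how often the rule matches what each tailored team targeted. Without this figure the supplementary result cannot be interpreted.
4. State that a factor-level null means only that the factor did not move on average over sites, and bring C14 into line with that.
5. C13a describes Aim 2 in the past tense, so label the addition post hoc if AT2 data have already been examined.

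The cost is plan wording and one derived variable from existing data. The downside is that the supplementary result names no single factor and loses power quickly as concordance falls.

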**Implementation.** We then piloted a standardized implementation protocol consisting of (a) embedding the PHQ-9 into the electronic health record (requiring the clinician to verbally assess clients as tablets were not available), (b) a site-specific guideline for PHQ-9 use, and (c) a brief training. The 4-hour training content was based on the work of Persons, Hong, and Koerner (2012); topics included: MBC as a foundational framework; MBC clinical utility; the research evidence for MBC and the PHQ-9; the MBC protocol; research and IT supports to enact the protocol; introduction to the electronic health record interface; and steps for working with lack of progress. These strategies reflect a minimum set of discrete evidence-based implementation strategies that could be blended to facilitate implementation. Pre-training Intention to Use MBC scores were highly correlated with the frequency of subsequent PHQ-9 administration ( $r=.67$ ,  $p=.036$ ). Across sites, 67% MBC penetration was achieved (number of clinicians implementing MBC/number of participating clinicians). Site A achieved 44% penetration while Site B achieved 80% penetration. One limiting factor at Site A was technology problems as the new electronic health record had not yet been introduced and the PHQ-9 did not consistently show up for clinicians. Despite these relatively high penetration scores at the clinician level, this minimal standardized implementation protocol and site-specified MBC guideline resulted in 13.4% (Site A) and 38.6% (Site B) use of the PHQ-9 (by dividing number of administrations by total possible number of administrations) over the course of one year follow up. Unfortunately, we were unable to assess the differential effect of MBC implementation on client outcomes to determine whether adapted guidelines limited MBC's utility. These findings support the proposal in three ways: (a) they emphasize the utility of a

mixed methods needs assessment in identifying site differences in barriers, (b) they highlight the importance of tailoring strategies to barriers as this minimal standardized protocol led to superior outcomes in Site B where fewer barriers were present, and, (c) they underscore the potential importance of incorporating technologically advanced solutions for client PHQ-9 completion.

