**Data Collection.** See *Table 5: Study Measures, Section II* for concise descriptions of the clinician battery. Each contextual factor of diffusion ([name] et al., 2008) will be assessed via self-report (and qualitatively via focus groups). MBC fidelity is the main clinician level implementation outcome. All clinician measures will be administered across three time points for each cohort with respect to their time since starting implementation: 1) Phase 1: Baseline Needs Assessment (AT1), prior to MBC implementation; 2) Phase 2: Implementation/Process Evaluation (AT2, 5 months in), following the active implementation phase; and, 3) Phase 3: Outcome/Impact Evaluation (AT3, 15 months in) 10 months after the research personnel have exited. Barriers to implementation will be collected for the first month of implementation via the electronic health record.

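### Aim 2 path b names no term for a clinician's PHQ-9 completion in months 1–5, so it cannot separate factors that drive sustained use from factors that merely accompany early use

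*Combined protocol and SAP*

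**What the plan says.** C13a splits mediation into two parts: "The two critical effects underlying mediation were evaluated in separate models". Path a is condition predicting the mediator; path b is the mediator predicting the outcome. On timing, "mediators were assessed at the conclusion of the implementation window and the mediators were used to predict PHQ9 completion in the sustainment window". C12a places the survey: "Implementation/Process Evaluation (AT2, 5 months in), following the active implementation phase". The Specific Aims give 5 months of active implementation and 10 of sustainment, so the outcome window is months 6–15.

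The model for path b is given in one sentence: "The b path was assessed using generalized linear mixed models with a logit link function for a binary distribution using the lme4 package". No covariate and no random effect is named. Neighbouring analyses are fuller. Path a is "implemented using the R lmerTest package with a random intercept for clinic", and Aim 3 starts from a "mixed model containing patient status as a covariate and random intercepts for patient and clinic". No lagged-outcome, change-score or sensitivity analysis is described for Aim 2.

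The data for an adjustment exist. C6 has PHQ-9 completion captured automatically in the electronic health record, and Table 5 has the surveys at baseline, month 5 and month 15. C13a also lists the drop-down reasons for deviating from MBC as mediators; C6 and C12a have these collected in the first month.

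**The concern.** Measuring the mediator before the outcome window protects against reverse causation only if the outcome behaviour has not yet begun. Here it has. By month 5 each clinician has had training, consultation and five months of opportunity to use the PHQ-9. That experience may colour answers on attitudes, norms and climate, and clinicians who used it early may simply continue. Path b then tests whether the month-5 score is associated with later use, and that association can exist when the score has no influence at all. A clinician random intercept, if one was intended, would not help, because it is assumed independent of the mediator.

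At stake is what Aim 2 is for. C16 promises to identify the contextual factors responsible for sustained MBC. A factor that follows from early use could be named as its cause. If condition changes early use, which H1a predicts, path a can be non-zero for the same factor.

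**Working it through.** **The plan's own Aim 2 figure.** C13a states detectable κ² of .16 (clinicians) and .10 (clients), using a design-effect-corrected sample size. With 12 sites and ICC .05:

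- Clinicians: 150/12 = 12.5 per site; design effect 1 + 11.5 × .05 = 1.575; effective n = 150/1.575 = 95.2.
- Clients: 500/12 = 41.67 per site; design effect 1 + 40.67 × .05 = 3.033; effective n = 164.8.

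With equal paths and 80% power, a Sobel test gives κ² of .150 and .091 without dropout, and .159 and .093 with 10% dropout. A joint-significance test gives .103 and .061. The plan does not state the test or the split between paths, so exact reproduction is undetermined. Nothing below depends on it.

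**Inputs for path b.** From the plan: 150 clinicians, 12 sites, site ICC .05, two-sided 5%. Assumed: r, the correlation of early use with the month-5 score (0 to .5); ρ, the correlation of use between windows (.5); 15 and 25 encounters per clinician in the two windows.

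**Model under no effect.** Score M = r·W1 + noise; later use W2 = ρ·W1 + noise; no path from M to W2. Then corr(M, W2) = r × ρ, which is not zero.

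**Approximate rejection rate if use were observed without error.** Noncentrality ≈ rρ/√(1 − r²ρ²) × √137, where 137 = 150 − 12 − 1.

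- r = .2: .10/.995 × 11.70 = 1.18, about 22%.
- r = .3: .15/.989 × 11.70 = 1.78, about 43%.
- r = .5: .25/.968 × 11.70 = 3.02, about 86%.

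**Simulated rates.** Completion is drawn as binomial counts and turned into empirical logits. Path b is a clinician-level regression with site effects, as a proxy for the mixed logit model. Sampling noise in the counts pulls the unadjusted rates below the approximation.

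| r | Path b rejects, unadjusted | With months 1–5 completion added |
|---|---|---|
| 0 | 5% | 5% |
| .2 | about 17% | about 6% |
| .3 | about 31% | about 8% |
| .4 | about 53% | about 9% |
| .5 | about 74% | about 15% |

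Repeat runs move these by a few points. The excess over 5% in the last column comes from error in the observed early rate.

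**Sensitivity.**

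- With ρ = .7, unadjusted rates at r = .2, .3 and .5 are about 28%, 56% and 96%.
- If the score follows the observed early rate, clinicians differ more and use is more persistent, the unadjusted rates are 43%, 82% and over 99%, against 4–6% adjusted. With fewer encounters, less spread or weaker persistence, r = .2 to .3 gives 10% to 70%, still 4–6% adjusted.
- If a stable clinician trait drives both score and use, adjustment leaves 12% at r = .3 and 28% at r = .5, against 83% and 100% unadjusted.

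**What adjustment costs.** At r = .3, detection of a true standardized effect of .2 goes from 96% to 79%; part of the 96% is the bias itself. If instead the factor truly drives months 1–5 use and acts later only through it, detection falls from 37%, 78% and 96% to 8%, 15% and 24% at correlations of .3, .5 and .67.

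**The case against.** The strongest reply is that the direction from use to attitude is assumed. That stands. A reader might take two figures in the documents as evidence for it, and neither is.

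- The .50 in "Repeated measurements were nested within participants (ICC = .50" is an input to the power simulation. It does not estimate how far PHQ-9 use persists, and it says nothing about use changing attitudes.
- The pilot result in C9, "Pre-training Intention to Use MBC scores were highly correlated with the frequency of subsequent PHQ-9 administration" (r = .67), has the factor before the behaviour. It shows that links of this size can occur, but in the direction the plan's theory expects.

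A reader might also take 17–74% as the chance of a false mediator. It is not, because path a must be significant too. If condition does not change early use, both paths reject in about 1–5% of trials. With a condition effect on early use of d = .46, the smallest the plan says it can detect for clinicians, the joint rate is about 1%, 3%, 8% and 11% at r = .2 to .5; the last moves by several points with the choice of path a test. It becomes large only for larger assumed effects (up to 34% at d = .8).

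Nor does the plan rule out adjustment; it is silent, and silent on path b's random effects as well.

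Finally, early use is post-randomisation and may lie on a genuine path from condition through the factor to sustained use. The adjusted model therefore answers a different question and can discard real mediators, as the detection figures above show. This rules out making the adjusted coefficient the only result. It does not rescue the unadjusted coefficient as evidence of cause.

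**Conclusion.** The point holds in a conditional form. As specified, path b cannot distinguish a driver of sustained completion from a consequence or companion of early completion. Under assumed early-use correlations of .2 to .5 and a window correlation of .5, it rejects in about 17–74% of trials with no effect, against about 6–15% after adjustment. With no relation between early use and the month-5 score there is no inflation. The size rests wholly on correlations that the documents do not give; the timing and the absence of a stated adjustment are in the text.

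The documents do not support saying that Aim 2 will produce false mediators at these rates, or that early use is known to shape the survey scores. The point applies to all the contextual factors surveyed at month 5, not only attitudes. It limits how mechanisms may be described and leaves the co-primary comparison untouched.

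**What to change.** For the month-5 survey mediators, fit path b twice: once without and once with the clinician's months 1–5 PHQ-9 completion from the electronic health record (completed over encounters, or its empirical logit). State the random effects for both fits, and report both coefficients.

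- Read the adjusted coefficient as the factor's effect on change into sustainment.
- Read the unadjusted one as an association that may include reverse causation.
- Say that a factor drives sustained use only where the adjusted coefficient supports it.
- Do not take a null adjusted result as ruling out effects already exerted through early use.

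Do not use this covariate for the drop-down barrier mediators. They are collected in the first month, so most months 1–5 completion comes after them.

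No new data are needed. The costs are some power, a changed estimand in the adjusted model, and residual bias from error in the observed rate or from a stable clinician trait. The baseline survey score is a natural further covariate for the last of these.
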